## 9.5. Secondary Endpoint Analyses

All secondary endpoints as described in Section 6.2.3 will be tabulated. Means, standard deviations and sample size will be used to summarize continuous characteristics. Distributions of continuous data will be examined and if non-normality is exhibited, medians and interquartile ranges will be presented. Percentages, raw number of subjects exhibiting a characteristic, and sample size will be used to summarize categorical characteristics. Measures collected serially over time (for example, ABI) will be presented at each time point, and the measure at each time point will be compared to the baseline measure as well as tested for trends. All available data will be used for each endpoint and no imputations will be done. The mITT analysis set will be used for these analyses.

### 9.5.1. Secondary Endpoints

The following endpoints will be summarized as noted above:

- Contribution of individual MAE rates for death, major amputation performed on the target limb and CDTLR to the overall MAE rate at 30 days.
- Long-term safety assessment – overall MAE rate at Month 12 and contribution of individual event rates to the overall MAE. Freedom from MAE will be additionally displayed via Kaplan-Meier plots.

- Overall rate and incidence of type of serious adverse events from Day 0 through completion of Study follow-up at Month 36.
- Technical success reported by the core lab as the percentage of treated lesions in which a final result of  $\leq 50\%$  residual diameter stenosis (in-stent) was achieved at index procedure.
- Primary stent patency rate: determined at Months 12 and 24 using values of: PSVR  $>2.0$ ;  $>2.4$ ;  $>2.5$ ; and  $>3.5$ , each to indicate loss of patency on duplex ultrasound or where angiography reveals  $>50\%$  diameter stenosis or where the subject undergoes CDTLR. When both imaging modalities are available, angiography takes precedence. ■
- Clinical outcome: comparison of Rutherford Clinical Category measured at Baseline, Day 30, Months 12 and 24. Worsening of Rutherford Clinical Category is defined as an increase by one or more categories compared to Baseline or unexpected major amputation of the target limb.
- Clinical outcome: comparison of Six-Minute Walk Test measured at Baseline, Day 30, Months 12 and 24 (sub-group of investigational sites).
- Functional outcome: comparison of the ankle brachial index (ABI) measurement at Baseline, within 30 days after index procedure, then at Months 12 and 24.
- Stent integrity measured as freedom from stent fracture, defined as clear interruption of a stent strut observed in a minimum of two projections, determined by core lab examination of X-rays taken with the leg in extension at 12, 24 and 36 Months.

#### 9.5.2. Walking Impairment Questionnaire

In addition to the individual scores, the following summary scores will be calculated. If more than half of the components of the score are missing, the score is considered missing. [6]

- Walking distance score =  $(20 * (\text{points for walking indoors})) + (50 * (\text{points for walking 50 feet})) + (150 * (\text{points for walking 150 feet})) + (300 * (\text{points for walking 300 feet})) + (600 * (\text{points for walking 600 feet})) + (900 * (\text{points for walking 900 feet})) + (1500 * (\text{points for walking 1500 feet})) / \text{total possible score}$ .
- Walking speed score =  $(1.5 * (\text{points for walking slowly})) + (2 * (\text{points for walking at average speed})) + (3 * (\text{points for walking quickly})) + (5 * (\text{points for running or jogging})) / \text{total possible score}$ .
- Stair climbing score =  $(1 * (\text{points for climbing one flight of stairs})) + (2 * (\text{points for climbing two flight of stairs})) + (3 * (\text{points for climbing three flight of stairs})) / \text{total possible score}$ .
- Overall score is the average of the three scores above. If any score is missing, the overall score is missing.

## 9.7. Safety Analyses

### 9.7.1. Adverse Experiences

All adverse events collected will be coded according to the study coding manual. Events will be summarized cumulatively through the following time points: in-hospital, 30 days, 12 months, 24 months and 36 months.

Frequency count of Adverse Events and unique number of patients who had the AEs, for each coded term, will be presented. Also, the frequency and percentage of patients who had a Serious AE (SAE), or a related AE (by relationship to both procedure and device) will be tabulated separately by coded term.

If a patient experienced multiple AEs, only the most severe event or the most intense relationship to treatment will be counted within a particular AE code.

CEC adjudicated events will be tabulated.

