### 6.2.3. Secondary Endpoints

1. Contribution of individual MAE rates for death, major amputation performed on the target limb and CDTLR to the overall MAE rate at 30 days.
2. Long-term safety assessment – overall MAE rate at Month 12 and contribution of individual event rates to the overall MAE.
3. Overall rate and incidence of type of serious adverse events from Day 0 through completion of Study follow-up at Month 36.
4. Technical success reported by the core lab as the percentage of treated lesions in which a final result of ≤50% residual diameter stenosis (in-stent) was achieved at index procedure.
5. Primary stent patency rate: determined at Months 12 and 24 using values of: PSVR >2.0; >2.4; >2.5; and >3.5, each to indicate loss of patency on duplex ultrasound or where angiography reveals >50% diameter stenosis or where the subject undergoes CDTLR. When both imaging modalities are available, angiography takes precedence.
6. Clinical outcome: comparison of Rutherford Clinical Category measured at Baseline, Day 30, Months 12 and 24. Worsening of Rutherford Clinical Category is defined as an increase by one or more categories compared to Baseline or unexpected major amputation of the target limb.

[REDACTED]

[REDACTED]

7. Clinical outcome: comparison of Six-Minute Walk Test measured at Baseline, Day 30, Months 12 and 24 (sub-group of investigational sites).
8. Functional outcome: comparison of the ankle brachial index (ABI) measurement at Baseline, within 30 days after index procedure, then at Months 12 and 24.
9. Functional outcome: comparison of the Walking Impairment Questionnaire at Baseline, within 30 days after index procedure, then at Months 12 and 24.
10. Stent integrity measured as freedom from stent fracture, defined as clear interruption of a stent strut observed in a minimum of two projections, determined by core lab examination of X-rays taken with the leg in extension at 12, 24 and 36 Months.

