#### 9.2.8. Analysis Windows and Definitions

Study subjects are required to return for clinic visits post-procedure at Day 30 ( $\pm 7$  days), Month 12 (365 days  $\pm 30$  days), and Month 24 (730 days  $\pm 60$  days). A final study visit at Month 36 (1095 days  $\pm 60$  days) is required as well; however, this visit may be completed either as a clinic visit or telephone visit. For ascertainment of the primary endpoints, if the subject is known to be event free at at least the lower limit of the visit window, that subject will be considered event free for the analysis. Thus, if a subject misses the 30 day visit, but is determined to have been event free up to the 12 month visit, then that subject will be considered event free. If the subject has no data past the lower boundary of the visit window, their data will be considered missing.

For the purposes of these analyses, 12 months is defined as 365 days post procedure, and similarly 24 and 36 months are defined as 730 and 1095 days, respectively. Procedure is considered day 0 so that days from procedure is defined as (visit date – procedure date).

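### Serious adverse events to Months 24 and 36 are planned as crude patient percentages, with no stated denominator and no allowance for unequal follow-up

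*SAP*

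**What the plan says.** Secondary endpoint 3 in SAP section 6.2.3 is: "Overall rate and incidence of type of serious adverse events from Day 0 through completion of Study follow-up at Month 36". Section 9.5.1 repeats it among the endpoints to be summarized.

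Three provisions set how it is reported:

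- Section 9.7.1: "Events will be summarized cumulatively through the following time points: in-hospital, 30 days, 12 months, 24 months and 36 months". SAEs are tabulated by coded term as the frequency and percentage of patients.
- Section 9.5, on the form of the summary: "Percentages, raw number of subjects exhibiting a characteristic, and sample size will be used to summarize categorical characteristics". On the analysis set: "The mITT analysis set will be used for these analyses".
- Section 9.5, on missing data: "All available data will be used for each endpoint and no imputations will be done".

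No Kaplan-Meier estimate, cumulative incidence, person-time rate or number at risk is named for SAEs.

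Time-to-event methods do appear elsewhere. For major adverse events (MAE), section 9.5.1 says: "Freedom from MAE will be additionally displayed via Kaplan-Meier plots". Section 9.8.2 specifies a Kaplan-Meier estimate of 36-month freedom from clinically driven target lesion revascularization (CDTLR), with a Greenwood 95% interval. Section 14 lists Kaplan-Meier figures for patency, MAE and CDTLR.

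**The concern.** Section 4 describes the two years after Month 12 as follow-up for medications and adverse events. Adverse events are therefore a main product of that period, and follow-up is least complete there. A crude percentage has to place a subject who leaves at, say, Month 14 without an SAE either in or out of the Month 36 denominator. Neither choice estimates the 36-month risk when there is attrition.

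The SAP deals with this for the primary endpoints. Section 9.2.8 sets a rule that begins: "For ascertainment of the primary endpoints, if the subject is known to be event free at at least the lower limit of the visit window". A subject with no data past the lower window is treated as missing. Section 9.2.3 adds a tipping point analysis, also for the primary endpoints. Neither provision is written for SAEs.

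At stake are the accuracy of the 24- and 36-month SAE figures and a choice of denominator that stays open until the data have been seen.

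**Working it through.** **Plan figures.** The SAP states no expected SAE rate and no Month 36 attrition, so there is no figure of its own to reproduce on this point. The gap between 271 enrolled and 230 evaluable (1 - 230/271 = 15.1%) concerns evaluability for 12-month patency, including availability of diagnostic ultrasound images. It is not Month 36 loss and is not used here.

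**Assumptions (not from the SAP).** True 36-month risk of a first SAE S = 50% or 60%. Loss for reasons other than death by Month 36 d = 10% or 20%. Constant hazards, with loss independent of SAE risk. Deaths count as SAEs.

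**Formulas.** Over the 36 months, let L = -ln(1 - S) and M = -ln(1 - d).

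- Crude percentage over all mITT subjects: C = L/(L + M) × [1 - exp(-(L + M))].
- Event-free and followed to Month 36: F = exp(-(L + M)) = (1 - S)(1 - d).
- Percentage among subjects with an event or complete follow-up: E = C/(C + F).

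**Worked case, S = 50%, d = 20%.** L = 0.6931, M = 0.2231, L + M = 0.9163, F = 0.5 × 0.8 = 0.40. C = (0.6931/0.9163) × 0.60 = 0.454. E = 0.454/(0.454 + 0.40) = 0.532.

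| True risk | Loss | All-mITT denominator | Error (points) | Event-or-completer denominator | Error (points) |
|---|---|---|---|---|---|
| 50% | 10% | 47.7% | -2.3 | 51.5% | +1.5 |
| 50% | 20% | 45.4% | -4.6 | 53.2% | +3.2 |
| 60% | 10% | 57.4% | -2.6 | 61.5% | +1.5 |
| 60% | 20% | 54.7% | -5.3 | 63.1% | +3.1 |

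**Wider range.** With S from 30% to 60% and d from 10% to 30%, the all-mITT figure is 1.4 to 8.2 points too low. The event-or-completer figure is 1.2 to 5.1 points too high.

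**Rare events, such as device-related SAEs (assumed S = 3% to 5%).**

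- S = 3%, d = 10%: L = 0.0305, M = 0.1054, F = 0.97 × 0.90 = 0.873. C = (0.0305/0.1358) × 0.127 = 2.85%, or 0.15 points low.
- S = 5%, d = 20%: L = 0.0513, M = 0.2231, F = 0.95 × 0.80 = 0.76. C = (0.0513/0.2744) × 0.24 = 4.49%, or 0.51 points low. That is 0.0051 × 271 = 1.4 subjects if all 271 were in the set.

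**The case against.** **The mechanism is not written.** A reader might infer that the plan declares early leavers SAE-free to Month 36, so that long-term harm is certainly understated. No section says so. The denominator at Months 24 and 36 is not stated, and section 9.5 bars imputation, which fits poorly with counting unobserved time as event-free. An event-or-completer denominator reverses the bias. This stands: understatement follows from the mITT reading and is likely, but not fixed by the text. It does not remove the problem, because both denominators misestimate the risk.

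**SAEs are not the only outcome handled this way.** A reader might also infer that they are the sole long-term event outcome left on a crude scale. Stent fracture at 12, 24 and 36 months, related adverse events and events adjudicated by the Clinical Events Committee are also tabulated. For MAE, the Kaplan-Meier plot is additional to a Month 12 rate. The only Kaplan-Meier point estimate specified with an interval is 36-month CDTLR, so the contrast with the rest of the plan is weaker than it first looks.

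**The effect may be small.** The inputs are assumed. The Month 36 visit may be done by telephone (section 9.2.8), which may limit loss. SAEs before exit are still counted. Withdrawals are tabulated with reasons (section 9.3) and exits are listed (section 13), so attrition is visible. For rare SAE types the absolute error is about one subject.

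**Nothing is decided on this endpoint.** It is descriptive, and patient percentages are a conventional presentation. This also stands, and it limits the severity. It does not make a crude percentage a sound estimate of 36-month risk when a better one costs little.

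**Conclusion.** The point holds in a limited form. The SAP gives cumulative SAE results to Months 24 and 36 as crude patient percentages. It fixes neither the denominator at each time point nor any method that allows for unequal follow-up.

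On the mITT reading, the 36-month percentage for any SAE is about 2 to 5 points too low, given an assumed 50-60% risk, 10-20% loss, constant hazards and independent loss. The relative shortfall at 20% loss is about 9-10% for common and rare events alike (4.6/50, 5.3/60, 0.51/5). In absolute terms it is about half a point or less for rare device-related SAEs. On an event-or-completer reading the sign reverses.

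The text does not support a claim that long-term harm in general is understated. MAE and CDTLR are also shown by Kaplan-Meier, and the direction for SAEs depends on an unstated choice. Severity is low to moderate: a named secondary safety endpoint is affected, but neither the primary endpoints nor study success.

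**What to change.** Keep the crude counts and percentages in section 9.7.1, and state the denominator and the number at risk at each time point.

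Add a table of the cumulative incidence of the first SAE at days 30, 365, 730 and 1095 with 95% confidence intervals:

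- any SAE, with death counted as an event: Kaplan-Meier;
- device-related and procedure-related SAEs: Aalen-Johansen, with death as a competing event.

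Name these in section 9.5.1 as the long-term rates for secondary endpoint 3.

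The cost is a few sentences in the SAP and one extra table from dates already collected. The reported long-term SAE rate may come out slightly higher. These estimates still assume that loss is unrelated to SAE risk, so the table should be read beside the withdrawal reasons already planned in section 9.3.

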### 9.7.2. Device Failures, Malfunctions

The number of device failures and malfunctions will be tabulated and included in a listing.

### 9.7.3. Concomitant Medications

Medication use will be summarized by at each study time point.

## 9.8. Post-Approval Study (36 Months)

### 9.8.1. Continued Follow-up of Pivotal Cohort

The MIMICS-2 IDE Study was designed as a 3-year follow-up study and will continue to assess subjects through completion of the 36-month visit, with the last subject due to exit the Study no later than Dec-2019. The follow-up assessments to be conducted at 36 months are outlined in the study protocol, CID 100 Issue 09 and these long-term follow-up data and conclusions will be reported within the final Clinical Study Report.

### 9.8.2. Primary Endpoint for Post-Approval Study

In addition to the previously specified MIMICS-2 IDE Study endpoints, a new 36-month primary endpoint is now defined as the rate of freedom from clinically driven target lesion revascularization (CDTLR), with clinical events adjudicated by the CEC. The 3-year rate of freedom from CDTLR will be estimated via Kaplan-Meier methods and presented along with the two-sided 95% confidence interval with error estimated via the Greenwood variance formula. Kaplan-Meier plots of CDTLR over time from Day 0 through Month 36 will be displayed.

[REDACTED]

[REDACTED]

**10. CHANGES TO ANALYSES PLANNED IN THE PROTOCOL**

The primary endpoint for the post-approval study has been defined as the rate of freedom from CDTLR at 36 months, as documented in Section 9.8 of this document.

## 12. STATISTICAL TABLES TO BE GENERATED

### Disposition/Demographics/Procedure

Table 1.1	Subject Disposition
Table 1.2	Subject Enrollment by Site
Table 2.1	Baseline Demographics
Table 2.2	Relevant Medical History & Risk Factors
Table 2.3	Baseline Demographics by Country
Table 2.4	Relevant Medical History & Risk Factors - By Country
Table 3.	Site Reported Procedure Details
Table 4.1	Site Reported Target Lesion Summary - Lesion Preparation / Pre-Dilatation
Table 4.2	Site Reported Target Lesion Summary - Stent Delivery System & Stent Deployment Procedure
Table 4.3	Site Reported Target Lesion Summary - Post-Treatment / Post-Dilatation of Target Lesion
Table 4.4	Site Reported Non-Target Lesion Summary

### Primary/Secondary Endpoints

Table 5.1	Primary Endpoints
Table 5.2	Primary Endpoints - SUBGROUP ANALYSIS (Region)
Table 5.3	Primary Endpoints - SUBGROUP ANALYSIS (Sex)
Table 5.4	Primary Endpoints - SUBGROUP ANALYSIS (US/OUS)
Table 5.5	Primary Endpoints - SUBGROUP ANALYSIS (Japan/ROW/Overall)
Table 5.6	Primary Endpoints - SUBGROUP ANALYSIS (Japan/US/Germany)
Table 5.7	Primary Endpoints - SUBGROUP ANALYSIS (Cilostazol)
Table 5.8	Primary Endpoints - SUBGROUP ANALYSIS (5mm Stent)
Table 5.9	Primary Endpoints - SUBGROUP ANALYSIS (Overlapping Stents)
Table 5.10	Primary Endpoints - SUBGROUP ANALYSIS (Age <70, >=70)
Table 5.11	Primary Endpoints - SUBGROUP ANALYSIS (Race)
Table 5.12	Primary Endpoints - SUBGROUP ANALYSIS (Race – Hispanic or Latino)
Table 5.13	Primary Endpoints - SUBGROUP ANALYSIS (Sites – Poolability)
Table 6.1	All CEC Adjudicated Events
Table 6.2	All CEC Adjudicated Events Related to Procedure
Table 6.3	All CEC Adjudicated Events Related to Device
Table 6.4	Primary Endpoint for Post-Approval Study
Table 7.1	Clinical Assessments at Follow-up Summary
Table 7.2	Clinical Assessments at Follow-up Pulses

### Safety

Table 8.	Medications - mITT Subjects
Table 9.0	Site Reported Adverse Events Summary
Table 9.1	Site Reported Adverse Events
Table 9.2	Site Reported Adverse Events Related to the Device
Table 9.3	Site Reported Adverse Events Related to the Procedure
Table 9.4	Site Reported Serious Adverse Events
Table 9.5	Site Reported Serious Adverse Events Related to the Device
Table 9.6	Site Reported Serious Adverse Events Related to the Procedure
Table 10.	Device Observation

**Core Lab / WIQ**

Table 11. Duplex Ultrasound

Table 12. X-Ray

Table 13.1 Follow-Up Additional Subject Assessments / 6-Minute Walk Test

Table 13.2 Walking Impairment Questionnaire Summary

Table 14.1 Baseline Angiography

Table 14.2 Baseline Angiography - QVA

Table 14.3 Baseline Angiography - Morphology

Table 14.4 Angiography – Stent Fracture

**Protocol Deviations**

Table 15.a Protocol Deviations Overall and by Time Point - ITT Subjects

Table 15.b Count of Protocol Deviations By Site Number

## **13. DATA LISTINGS TO BE GENERATED**

### **Disposition**

- Listing 1.1 Subject Disposition / Enrollment
- Listing 1.2 Listing of Subjects Exiting the Study
- Listing 2. Listing of Reasons for Exclusions from ITT
- Listing 3. Listing of Inclusion/Exclusion Criteria

### **Demographics, Baseline and Procedural Characteristics**

- Listing 4. Demographics and Medical History
- Listing 5.1. Procedure - General
- Listing 5.2: Procedure - Non-Target Lesions
- Listing 5.3: Procedure - Target Lesion

### **Endpoints**

- Listing 6. Duplex Ultrasound Core Lab and Primary Patency Results
- Listing 7. CEC Adjudication Results
- Listing 8.1 Physical Exam (Baseline)
- Listing 8.2 Rutherford class, Pulses and ABI/TBI Recordings
- Listing 9. Follow-Up Additional Subject Assessments / Walking Impairment Questionnaire
- Listing 10. X-Ray

### **Adverse Events**

- Listing 11.1 Listing of Adverse Events
- Listing 11.2 Listing of Adverse Events Reported Post 12 Month Visit Window

### **Other Safety Data**

- Listing 12. Medications
- Listing 13. Device Observation
- Listing 14. Protocol Deviations
- Listing 15.1 Angiography - Morphology
- Listing 15.2 Angiography - QVA
- Listing 16. Angiography Safety Adjudication

## 14. FIGURES TO BE GENERATED

Figure 1a. Tipping Point Analysis for the Primary Effectiveness Endpoint: Patency

Figure 1b Tipping Point Analy for the Primary Safety Endpoint: MAE

Figure 2. Kaplan Meier Analysis of Primary Patency

Figure 3. Kaplan Meier Analysis of Adjudicated MAE

Figure 4. Kaplan Meier Analysis of Adjudicated Clinically Driven TLR
